5.1 General Considerations

Statistical analysis of this study will be the responsibility of the sponsor or its designee. All tables, figures, and listings will be created using the data described in Table 1 and Section 4.7 (unless otherwise noted), including data during study participation. While not reflected in a table, figure, or listing, any data collected after study participation (e.g., in the Lilly Safety System or collected through queries to the investigator) may be discussed in a clinical study report (CSR) or integrated summary document when deemed relevant. Unless otherwise noted, displays will include columns for study participants and controls will be displayed.

Not all displays described in this statistical analysis plan (SAP) will necessarily be included in the CSR. Not all displays will necessarily be created as a “static” display. Some may be incorporated into interactive display tools instead of, or in addition to, a static display. Any display described in this SAP and not provided would be available upon request.

Treatment differences will be evaluated based on a two-sided significance level of 0.05 for all efficacy analyses. Ninety-five percent confidence intervals for the estimated event rate, odds ratio/hazard ratio will be provided. While we describe many methods addressing different uncertainties, we may not need to perform all analyses mentioned in the draft. Additional exploratory analyses of the data will be conducted as deemed appropriate. All statistical analyses will be performed using R 3.6 (or a higher version).

5.1.1 Populations for Analyses

We define the analysis populations in Table 3 along with the analysis we will conduct. All patients meet the study eligibility criteria. Note that all populations for analyses are UHC members, and the following proposed analytical methods are for UHC members. We may see non-UHC members satisfying the study eligibility criteria, but we cannot obtain or have very limited information of their comorbidities, demographic (e.g., area of residence, socioeconomic index), and if having immunosuppressive treatment prior to COVID-19 diagnosis.

Table 3. Population for analyses

Population	Data for analysis	Definition/Data
Study participants	Disposition analysis and safety	Study participants who sign informed consent and receive Bamlanivimab in single infusion of 700 mg.
Pool of potential controls	Formation of the control group Pre-matching identification of risk factors Estimation of prognostic scores	Patients who meet the study eligibility criteria but did not receive Bamlanivimab.

Commented [WWY23]: Would suggest to revise to include general results reporting, definition of the analysis populations, analysis methods, definition of baseline Refer to attached sample SAP

Overall population	Descriptive analyses Propensity score matching	Consists of study participants and pool of potential controls.
Propensity score matched population	Efficacy and descriptive analyses	Subset of the overall population consisting of study participants and matched controls after propensity matching.
Double score (propensity score and prognostic score) matched population	Sensitivity analyses	Subset of the overall population consisting of study participants and matched controls after double matching.

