5.8.1.2 Propensity score matching

Objective:	Data Variables:	Data Source:
Construct a control group for study participants	
 • Flag of infusion treatment • Symptomatic flag • Demographic • Elixhauser conditions 	
 • Optum infusion pharmacy data • UHC claims data • CDSM • BCRT

- Optum EMR data

The objective of propensity score matching is to ensure balance between the treatment and control group on the selected covariates. Propensity score matching will be conducted after the completion of treatment enrollment (28-day study period) and upon the availability of information of study participants. Data sources of information for calculating the propensity scores for study participants will be Optum infusion pharmacy data, UHC claims data, and CDSM data. Note for the matched controls we will select them from Optum EMR+claims dataset, we will include only members who are COVID diagnosed, have documented symptoms of COVID-19, meet the inclusion/exclusion criteria for the study, and have historical information about selected risk factors (either through claims or EMR).

According to the current study eligibility criteria in Section 4.4.1, the treatment group consists of both UHC and non-UHC members. While UHC patients with continuous enrollments have pertinent historical information (i.e., comorbidity, demographic), accruing such information might be challenging and is likely unavailable for non-UHC members. We will first perform matching for the UHC-treated members with complete information. Next, we will exclude the selected matched-control individuals for each UHC-treated from the control set. The non-UHC patients will be matched sequentially case-by-base from the remaining control group for each outstanding treated participant using “exact” matching method based on available information. Note that, such exact matching for patients without relevant comorbidity variables may result in sub-optimal match.

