The following description of matching methods is for UHC members in the treatment group. We will apply propensity score matching techniques described in (Guo, 2014), and fit a GLM using matching covariates as selected risk factors of COVID-19 hospitalizations from Section 5.8.1.1 and response as the log odds of receiving treatment with a logit link, and estimate balancing (i.e., propensity) scores which are next to be used in finding the matched pair between treatment and control group. Model performance will be evaluated by pseudo R-square values (e.g., McFadden) and Hosmer-Lemeshow test. We will use nearest neighbor matching with a caliper which its size will be determined empirically. Note this matching model is different from 5.8.1.1 in terms of response (hospitalization flag vs receiving treatment). We will evaluate balance in covariates between study participants and matched controls by absolute standardized difference in mean (Austin, 2009) and variance ratio of propensity score and covariates since it is more robust in terms of sample size and covariate distribution requirements in comparison to other balance diagnostics (Ali, 2016). We will also conduct a hypothesis test to examine if a significant difference in matching covariates exists between treatment and control groups, such as Wilcoxon rank-sum (Mann-Whitney) test or *t*-test for continuous variables and Chi-squared test for categorical variables. We will use these tests to evaluate covariate balances before and after matching and repeat the processes if covariate imbalances remain.

We will consider nearest neighbor matching within a caliper (Smith, 2005), and obtain 1-to-1 match. As an alternative approach, optimal matching technique may also be adopted, in the event that the covariate imbalances persist using the prior methods. In addition, greedy matching methods make decisions about inclusion of a pair of treated-control participants as a matched set sequentially; here decisions are made one at a time without reconsidering early decisions as later ones are made. From this point of view, such mechanism is not optimal and therefore optimal

Commented [XM32]: Please describe in detail on how to estimate PS. Use the variables selected from 5.3.2.1 or redo the model selection?

Commented [JAT33R32]: Variables selected from the previous section. Added this specification in the second sentence of this paragraph.

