In addition, we will use double score matching (Yang, 2020), where matched controls are identified using both propensity and prognostic scores, rather than the propensity score only. We want to emphasize that the model-based matching (i.e., propensity and dual matching) are only applicable for UHC members; we will not have information available for all prognostic factors to calculate model-driven scores for non-UHC members. We will compute the propensity score as described in Section 5.8.1.2. The prognostic score is defined as the predicted outcome under the control group. It is estimated by modeling the COVID-19 related hospitalization using only the pool of potential controls, and then using the model to obtain the prediction of potential outcomes for the treatment group. Aside from the modeling method (logistic regression) described in Section 5.8.1.1, we also consider ensemble-based machine learning models (e.g., gradient boost, random forest, bagging, and support vector machine). We randomly split the historical cohort data (i.e., dataset described in Section 5.8.1.1 iteration 1) data into a training and test set (i.e., 80%-20%) ensuring the same proportion of cases (i.e., the observed number of hospitalization in control group divided by the total number of COVID cases) in each cohort. Next, we develop the models based on the training set, and evaluate their performances on the test set. We repeat the process 100 times, report the average classification metrics, and select the model that provides best numerical performances in terms of the prediction accuracy of the test set (e.g., F1 score, Area under the curve (AUC) of a receiver operating characteristic (ROC), balanced accuracy, and positive-predictive value (PPV)). Next, we exploit the full data set (without splitting) to train the final model which is to be used to generate prognostic scores for both treated and potential control participants. We will repeat the primary analysis using the double-score-matched study participants and controls. An R-package “dsmatch” will be used to perform matching and assess treatment efficacy after calculating propensity and prognostic scores.

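### The SAP leaves open whether non-UHC participants count in the primary efficacy analysis, and its UHC-only sentence conflicts with its own safety population

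*SAP*

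**What the plan says.** **Who is analysed.** SAP 5.1.1 introduces Table 3 with "Note that all populations for analyses are UHC members, and the following proposed analytical methods are for UHC members". The reason given is that comorbidity, demographic and prior immunosuppressant data are missing or very limited for other patients. Two rows of Table 3 matter here:

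- Disposition and safety: "Study participants who sign informed consent and receive Bamlanivimab in single infusion of 700 mg". The row has no insurance condition.
- Efficacy: "Subset of the overall population consisting of study participants and matched controls after propensity matching".

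**Who is matched.** SAP 5.8.1.2 says that "the treatment group consists of both UHC and non-UHC members". UHC participants are matched first. Then "The non-UHC patients will be matched sequentially case-by-base from the remaining control group for each outstanding treated participant using" exact matching on whatever information exists. The SAP concedes that "such exact matching for patients without relevant comorbidity variables may result in sub-optimal match". It then introduces the propensity-score method with "The following description of matching methods is for UHC members in the treatment group". SAP 5.8.2 says that propensity and double-score matching "are only applicable for UHC members".

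**Outcome sources.** SAP Table 1 marks claims and BCRT as available for UHC members only. SAP 4.7 lists BCRT as the participants' source for admission data. SAP 5.8.1.3 names infusion pharmacy data and BCRT for short-term capture of treated admissions, and claims and EMR for controls.

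**Eligibility.** Neither protocol 5.3 nor SAP 4.4.1 requires UHC membership. Protocol Appendix 1 records at registration whether a person has UHC insurance, so non-UHC participants are foreseen.

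**The concern.** The statements in 5.1.1 and 5.8.1.2 are both current text and cannot both govern. The primary comparison in 5.8.1.3 refers only to study participants and matched controls, and mock Table A9 has no split by insurer. Section 5.8.1.3 fixes a single model before outcome data are accessed, but no section fixes a single population. In an open-label study with external controls, that leaves a choice on the primary endpoint that could be made after results are seen.

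If the non-UHC pairs enter the primary comparison, four things follow:

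- Comorbidity is not balanced in those pairs by design.
- Their treated admissions are not covered by BCRT or claims. SAP 4.5 scores a participant with no COVID-19 admission as 0 on the binary endpoint, so a missed admission becomes a non-event.
- The adjusted models (SAP 5.2 and 5.8.1.3) need comorbidities. Under SAP 5.8.3, cases with missing features are dropped if they are fewer than 5% of the sample and imputed otherwise. Unadjusted and adjusted results could then cover different patients.
- The double-score analysis is UHC-only. If it disagreed with the primary result, the cause could be the method or the population.

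The safety issue is separate. The word *all* in the 5.1.1 sentence sits directly above a safety row that covers everyone infused. Describing the safety of at-home infusion is a primary objective in protocol section 2, so the denominator should not be in doubt.

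**Working it through.** **1. Where an exact-matched non-UHC pair belongs**

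| Place | Status of the pair |
|---|---|
| SAP 5.1.1 lead-in | Outside every analysis population |
| Table 3, efficacy row | Defined by propensity matching, so not included |
| SAP 5.8.1.2, opening | In the treatment group and given a matched control |
| SAP 5.8.1.2, method; 5.8.2 | Outside propensity and double-score matching |
| SAP 5.8.1.3 and Table A9 | Not stated |

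The pair is created but assigned to no population.

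**2. The plan's own sample-size figure**

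Inputs from SAP 4.3: two-sided 5% level, 90% power, 1:1 ratio, two-sample proportions with continuity correction. With d = p1 − p2 and p̄ the mean of the two rates:

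- n = [1.960·√(2p̄(1−p̄)) + z(power)·√(p1(1−p1) + p2(1−p2))]² / d²
- corrected n = (n/4)·[1 + √(1 + 4/(n·d))]²

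For the 75% row, p1 = 0.25 and p2 = 0.0625. This gives n = 77 per group, corrected to 88, for a total of 176 against the stated 175 (a rounding difference). The other nine rows of Table 2 also reproduce. No stated figure is wrong.

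**3. The fallback size in SAP 4.4.2** (1,000 per group, 15% versus 10%, power 0.8)

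- n = [1.960·√0.21875 + 0.8416·√0.2175]² / 0.05² = 1.714/0.0025, or 686 per group; 726 with correction.
- Power at 1,000 per group = Φ[(0.05·√1000 − 0.9167)/0.4664] = Φ(1.425) = 92.3%; 91.3% with correction. McNemar's test with independent pairs gives 92.2%.

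**4. Power if the primary set is UHC-only**

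The non-UHC share f is not in the documents, so every value is an assumption. Pairs = 1000·(1 − f), taking every UHC participant as matched. The figure of 1,000 is also the point at which SAP 5.13 runs the primary analysis.

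| f | Pairs | Power, uncorrected | Power, corrected |
|---|---|---|---|
| 0% | 1,000 | 92.3% | 91.3% |
| 10% | 900 | 89.4% | 88.1% |
| 20% | 800 | 85.7% | 83.9% |
| 30% | 700 | 80.8% | 78.5% |
| 40% | 600 | 74.6% | 71.7% |
| 50% | 500 | 66.7% | 63.2% |

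The 80% limits are 1 − 726/1000 = 27.4% (corrected) and 1 − 686/1000 = 31.4% (uncorrected).

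**5. What can be said about bias if the pairs are included**

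Suppose there is no treatment effect, control risk is the same in both groups of pairs, and non-UHC treated patients have r times the observed risk of their controls. Then the pooled risk ratio is (1 − f) + f·r. With r assumed between 0.6 and 1.5, it runs from 0.96 to 1.05 at f = 10% and from 0.88 to 1.15 at f = 30%. Neither f nor r is documented, so this shows only that size and direction are open.

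**6. Safety denominator under the literal reading**

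With 1,000 infused, f = 10%, 20% or 30% would leave 900, 800 or 700. The one-sided 95% upper bound after zero events is 1 − 0.05^(1/n). It would rise from 0.30% to 0.33%, 0.37% or 0.43%.

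**The case against.** The strongest reply is that Table 3 already settles efficacy. The efficacy set is the propensity-matched population, that matching is UHC-only, and so non-UHC pairs never reach the primary comparison. This is a reasonable reading and is close to the fix below. It does not close the point, because 5.8.1.2 still builds those pairs, calls their members part of the treatment group, and gives them no other use. A reader might infer that they will enter the primary result; the documents do not say so, and the efficacy consequences are conditional on it.

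A reader might also infer that infused non-UHC participants are dropped from safety. The documents do not support that as a settled exclusion. The Table 3 row has no insurance condition, the reason given for the UHC-only sentence concerns data needed for matching, and the infusion pharmacy source is not marked UHC-only. What remains is a conflict between a sentence and the table below it. The efficacy harms need 5.8.1.2 to prevail and the safety harm needs 5.1.1 to be taken literally, so they should not be added together.

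Two further replies have some force. The SAP calls non-UHC comorbidity data likely unavailable, not certainly absent, and protocol Appendix 1 collects some items at pre-enrolment, such as height, weight, cancer and transplants. Table 1 describes BCRT as complementary to infusion pharmacy data for participants' admissions, and participants have daily checks to Day 28. Non-UHC capture may therefore be weaker, but the documents do not show by how much.

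**Conclusion.** The conflict is real and nothing else in the two documents resolves it: membership of the primary efficacy set is undefined for non-UHC participants. It should be settled before outcome data are accessed. For safety, the finding is an internal inconsistency and not an exclusion.

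The size of any bias cannot be derived, because the non-UHC share, the imbalance in those pairs and the extent of missed admissions are all undocumented. A reader might infer a definite bias in favour of the drug; the text does not support a direction or an amount. The sample-size figures stand. The power figures rest on 1,000 infused, rates of 15% and 10%, complete matching of UHC participants, and assumed shares.

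**What to change.** 1. In SAP 5.1.1, limit the UHC-only sentence to the propensity-score matched and double-score matched (efficacy) populations.
2. In 5.1.1 and 5.8.1.3, state that the primary efficacy analysis uses the propensity-matched UHC participants and their controls.
3. Move the exact-matched non-UHC pairs from 5.8.1.2 to a labelled supportive analysis in 5.8.2, giving the matching variables and the outcome source.
4. State in Table 3 that safety and disposition cover all infused participants regardless of insurer.

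The cost is SAP wording and a smaller primary set. From 1,000 infused, power for 15% versus 10% stays at or above the SAP's 0.8 up to a non-UHC share of about 27% (corrected) or 31% (uncorrected). At 40% it is about 72–75%. SAP 4.4.2 says that participants without a match are lost, so power could be lower still. The sponsor should therefore check the actual non-UHC share and, if it is high, count the 1,000 in matched UHC participants. Including the non-UHC pairs could also be defended if fully specified in advance, but it would carry the weaker matching and outcome capture into the primary result.

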7.2 Benefits

There is no guarantee of direct benefit from participating. The study will test the hypothesis that treatment with Bamlanivimab (LY3819253) will reduce the incidence of COVID-19 related hospitalization and mortality in mild or moderate COVID-19 patients who are at high risk of progressing to severe COVID-19 and/or hospitalization, relative to matched external controls. The study will further describe the incidence of infusion related reactions and patient reported adverse events in patients treated with Bamlanivimab (LY3819253).

Given the available data and the recent emergency use authorization of Bamlanivimab (LY3819253) in this patient population, the benefit-risk assessment for this study is favorable.

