4.4 Study Population

4.4.1 Selection Criteria

Both study participants and matched controls will meet the inclusion and exclusion criteria below.

Inclusion Criteria:

- Age 65+, confirmed SARS-CoV-2 positive, located in an area where Bamlanivimab (LY3819253) is available for infusion
- Have mild or moderate COVID-19 symptoms (after stage 1 of symptom tracking)

Commented [JAT4]: Update to keep the same criteria in the latest protocol (version 10 on Feb 3, 2021).

Commented [JAT5]: Remove it as it is no necessary for active participants and controls.

- Control only: Confirmed symptomatic COVID-19 through Optum EMR data.

Exclusion Criteria:

- Current (from first symptom report) hospitalization for COVID-19
- Prior administration of Bamlanivimab

Commented [JAT6]: Remove as not necessary per the EUA.

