4.5 Endpoints

The following definitions of endpoints hold for all analyses described in this statistical analysis plan. For study participants, we define the study endpoint as 28 days after date of the Bamlanivimab infusion. This holds for both outcomes of COVID-related hospitalization with or without time consideration (i.e., no censoring vs censoring at Day 28). For example, if a study participant hasn't been hospitalized due to COVID-19 within 28 days after COVID-19 diagnosis, we'll treat the binary response of COVID-19 hospitalization as 0 without time consideration. However, with time consideration, it becomes right-censored since this participant may be hospitalized 29 or more days after COVID-19 diagnosis and our observation period is 28 days after COVID-19 diagnosis. More details are described in Section 5.8.1.3. For the pool of potential controls, we define the study endpoint as 28 days after a synthetic date of treatment. We will randomly select a number from the distribution of number of days after date of symptoms onset in study participants to identify an index date with which to define 28 days post infusion where we will monitor claims and EMR data for hospitalizations and mortality.

Commented [WWY14]: Should be the pool of controls which was before PS matching.

Figure 3 illustrates the timeline for study participants and controls to ensure alignment on an index date for symptoms onset and the follow-up period. Since the control group will not have an infusion date associated with them, we will randomly select a number from the distribution of number of days after date of symptoms onset in study participants to identify an index date with which to define 28 days post infusion where we will monitor claims and EMR data for hospitalizations and mortality.

[figure not shown]

Figure 3. Illustration of the timeline for study participants and controls.

For patients who do not experience a COVID-19 related hospitalization by Day 28 following the date of infusion or synthetic treatment, a censoring date is defined as the earliest of 28 days following the date of treatment, or for study participants, the early discontinuation date due to lost to follow-up.

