4.7 Variables/Measures

The primary outcome of interest is COVID-related hospitalization rate in study participants and matched controls. We list all potential covariates in two phases. Phase I covers historical data and Phase II includes post COVID-19 diagnosis information. Phase I historical data will be

collected for both study participants and matched controls. Phase II post-COVID 19 diagnosis data has two parts: data elements to be collected for both study participants and matched controls (Phase II.A), and data elements to be collected for only study participants (Phase II.B).

Phase I - Historical data: Study participants and matched controls:

1. COVID-19-related information:

Variable	Data source for study participants	Data source for matched controls
Date of COVID-19 diagnosis test	ProtectWell	Optum EMR or CDSM
Type of COVID-19 diagnosis test*		
Symptomatic flag during COVID-19 test	ProtectWell (all study participants are symptomatic)	Optum EMR
Previous COVID diagnosis flag	CDSM	Optum EMR or CDSM
Previous receipt of Bamlanivimab	UHC claims	Optum EMR or UHC Claims

*: Please see Table A1 in Appendix 1 for LOINC codes of the PCR and antigen COVID-19 tests.

Commented [WWY15]: This variable won't be used for analysis.

Commented [JAT16R15]: Not necessarily. We'll use it to approximate date of symptoms onset and identify matched controls who got COVID-19 around the same time. Please see the comment below for more details.

Commented [WWY17]: Would also include COVID-19 symptoms, and a timing variable: duration since symptom onset to index date

Commented [JAT18R17]: We will include these data fields if available. Regarding date of symptoms onset, it's approximated to be 2 days prior to date of COVID-19 diagnosis (1 day for overnight shipping of COVID-19 test kit and the other day for PCR test).

2. Demographic:

Variable	Data source for study participants	Data source for matched controls
Age as of 2021*		
ZIP code of residence (may or may not be used for identifying matched controls)		
Urbanization of residence in a zip code level (urban, suburban, rural)		
Region/State of residence		
Race		
Gender		
Flag determining whether a patient resides in a nursing facility – determining a patient does not live at home		

*: Age = 2021 – birth year.

Commented [WWY19]: As obesity is a high risk factor, suggest to include BMI as a covariate in PS matching

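### SAP Table 3 puts no date on the controls' non-receipt of bamlanivimab, so read literally it selects controls on treatment received after their index date

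*SAP*

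**What the plan says.** SAP 5.1.1, Table 3, defines the pool of potential controls as "Patients who meet the study eligibility criteria but did not receive Bamlanivimab". It gives no date, window or reference to the index date.

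SAP 4.4.1 applies to participants and controls alike. It excludes "Prior administration of Bamlanivimab" and "Current (from first symptom report) hospitalization for COVID-19", and requires everyone to be "located in an area where Bamlanivimab (LY3819253) is available for infusion".

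SAP 4.5 gives each control a synthetic treatment date. The plan is to "randomly select a number from the distribution of number of days after date of symptoms onset in study participants to identify an index date", then follow the control for 28 days. The censoring rule there names only Day 28 and, for participants, loss to follow-up.

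SAP 4.7 lists "Previous receipt of Bamlanivimab" among the Phase I (historical) variables. Phase II.A, the post-diagnosis data shared by both groups, has no field for bamlanivimab receipt. Infusion date appears only in Phase II.B, for study participants.

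Two further statements bear on whether controls could be treated. Protocol 7.2 refers to the "recent emergency use authorization of Bamlanivimab (LY3819253) in this patient population". An author reply in a margin comment at SAP 4.7 says the diagnosis date will help "identify matched controls who got COVID-19 around the same time".

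**The concern.** The eligibility list already removes anyone treated earlier. If the Table 3 clause adds anything to that list, it adds non-receipt at some later time, with no end date. Membership of the control group would then depend on what happens after follow-up has started.

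That matters because the chance of being infused later may depend on the outcome. If usual-care infusion is given only to outpatients, a control admitted soon after the synthetic date can no longer be infused and is sure to be retained. A control who stays out of hospital long enough to be infused is dropped. The retained pool is then enriched for early admissions, and the control rate rises even if the drug does nothing.

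Requiring every control to be out of hospital at index does not remove this, because the selection acts after index. Propensity matching on baseline covariates (SAP 5.8.1.2) cannot correct it. The E-value, proportion-of-unmeasured-confounding and double-score analyses (SAP 5.8.2) are not aimed at it.

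**Working it through.** The plan gives no figure on this point, so there is none to reproduce. SAP 4.4.2 supplies a scale: a fallback of 1,000 per group, planned for 15% against 10%.

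**Step 1: direction, by formula.** Assume no drug effect and let
- h = true 28-day risk
- e = share of hospitalizations that come before the later infusion would have happened
- q = share of still-unhospitalized controls infused after index and dropped

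Observed control rate = [h·e + h(1−e)(1−q)] / [h·e + (1−h·e)(1−q)].

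With h = 0.15, e = 0.5 and q = 0.20:
- numerator: 0.075 + 0.075 × 0.8 = 0.135
- denominator: 0.075 + 0.925 × 0.8 = 0.815
- observed rate: 0.135 / 0.815 = 16.6%
- false risk ratio: 0.15 / 0.1656 = 0.91

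The ratio is 1.00 when q = 0 and falls below 1 whenever q and e are both positive. Neither q nor e is in the documents.

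**Step 2: size, by simulation.** Assumptions, none taken from the documents:
- 15% would-be hospitalization, at a mean of 7 days from onset (gamma, shape 4)
- usual-care infusion uniform on days 2–10, and only before admission
- synthetic lag uniform on days 2–10
- every control unhospitalized at index
- no drug effect; 4 million patients per cell

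| Uptake among controls | False risk ratio, never-received pool | Two-sided rejection at 1,000 per group (nominal 5%) |
|---|---|---|
| 5% | about 0.99 | about 5.1% |
| 10% | about 0.97 | about 5.4% |
| 20% | about 0.95 | about 6.9% |
| 30% | about 0.91 | about 10.5% |

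At 20% uptake the at-risk 28-day rate is 9.06%, against 9.58% in the never-received pool: 9.06 / 9.58 = 0.946. Would-be hospitalization of 10% or 25% gives similar ratios.

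Uptake here counts infusion at any time on days 2–10. Because lag and infusion day share the same distribution, about half of it falls after index. In Step 1, q counts post-index receipt only, so the two scales should not be mixed.

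**Step 3: does dating the rule to index suffice?** At 20% uptake, dropping only controls infused on or before the synthetic date gives 9.29%, and 9.06 / 9.29 = 0.975. A residual remains because controls with a long lag have had more time to be infused, so those left have shorter lags (mean 5.76 days against 5.91). A shorter lag leaves more of the admissions still to come. Standardising on lag returns the ratio to 1.00.

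**Step 4: cost of keeping later recipients if the drug works.** Take true rates of 15% and 10% with q = 0.20 and e = 0.5. Later recipients carry 0.15 × 0.5 × 0.2 = 0.015 of the control risk. If a third of that is averted, the control rate is 0.15 − 0.005 = 14.5%, the risk ratio 0.10 / 0.145 = 0.69 (true value 0.67), and power at 1,000 per group about 0.87. A never-received pool gives 0.10 / 0.166 = 0.60.

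**The case against.** A reader might infer that the SAP definitely specifies a never-treated rule and that the primary result will therefore favour the drug. The documents do not support that, for four reasons.

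- **The clause may only separate the arms.** Participants meet the same eligibility criteria, including no prior receipt. The Table 3 row above defines them as those who receive the drug, and the overall population is the sum of the two rows. This reading is fair. It shows an ambiguity but does not resolve it, since no section ties non-receipt to the synthetic date.
- **The variable list points the other way.** SAP 5.1 says outputs use the data in Table 1 and Section 4.7 unless otherwise noted, and 4.7 holds only previous receipt. A pool built from that variable would not drop later recipients, and this bias would not arise. They would, however, be counted as untreated with no record of how many there are.
- **Uptake and the outpatient limit are not documented.** The availability criterion also has a logistical meaning: Protocol 6.2 and Appendix 1 tie it to where the study's home infusion can be delivered. It does not establish usual-care access for controls. That infusion stops at admission is inferred from the trial's own exclusion, not stated for usual care.
- **The effect is modest at low uptake.** It is about 1% on the risk ratio at 5% uptake, against planned reductions of 33% (SAP 4.4.2) and 75% (SAP 4.3). The Step 1 formula with q of 20–30% and e = 0.5 gives rejection rates of 16–36%. Those follow from that choice of q and e and should not be read as the expected error rate.

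What stands is that the plan allows two different control pools and does not choose between them.

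**Conclusion.** The point holds as a gap in the definition, with a conditional bias. Taken literally, Table 3 selects controls on exposure after index. If controls are infused in usual care after index and only before admission, the bias is toward the drug: a false risk ratio of about 0.99 to 0.91 over 5% to 30% uptake, under the Step 2 assumptions. At 5% uptake it is negligible; at 20–30% it is large enough to matter beside a planned 33% reduction. Uptake is unknown, so neither the presence nor the size of the bias is established. The definition should be settled before outcome data are accessed, because the choice affects the primary comparison and costs little to make.

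**What to change.** - **Table 3:** define the pool as patients who meet the criteria and have not received bamlanivimab on or before the synthetic treatment date. Keep later recipients in the primary binary comparison.
- **Lag:** after exclusions, make the controls' onset-to-index lag distribution match the participants' by matching or standardising on lag, or by redrawing it. Dating the rule to index is not enough alone (about 0.975 at 20% uptake).
- **SAP 4.7, Phase II.A:** add the date of any bamlanivimab receipt through Day 28 for controls, from claims or EMR, and report the proportion. These sources are already named for previous receipt.
- **Sensitivity analysis:** in the Kaplan-Meier and Cox analyses only, censor controls at infusion with inverse-probability-of-censoring weights, and add this to the censoring rule in SAP 4.5. Censoring has no defined meaning for the binary endpoint tested with McNemar's test.

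The cost is revised wording, one extra data extraction and one extra analysis. The statistical price is a slight dilution of the contrast if the drug works (Step 4). The reported proportion and the censored analysis would help show how much.
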